Dressings will be changed per institutional SOC guidelines but at a minimum of every 3 days. Subjects will return to the clinic on days 14 ± 3 and 28 ± 3 post-enrollment for the first 4 weeks and at months 3 (± 7 days), 6 (± 7 days), and 12 (± 14 days) post-enrollment. Subjects will also participate in a remote visit on days 7 ± 3 and 21 ± 3 post-enrollment. Dressing changes will be continued until reepithelialization is achieved. During each visit, study staff will document the number of dressing changes that occurred outside of clinic visits as well as any pertinent information related to the dressing changes. During visits when dressing changes are still necessary, subjects will complete the VAS pain score before and after dressing changes to each burn, and any unanticipated adverse events related to the device will be logged. Subjects who are able and willing will download an application on their smartphone that will prompt them to record the VAS pain score before and after dressing changes will complete this during remote visits on days 7 and 14. Subjects will also be asked to upload photos of the burns at days 7 and 21 utilizing the medical center's MyChart application. Appearance of the sites will be assessed at months 3, 6, and 12 using the POSAS. During the visits at 3, 6, and 12 months, sites will be subjected to 3 measurements of TEWL. Photographs will be obtained at all in-person visits and may be subjected to wound closure and percent epithelialization measurements via ImageJ. Recording of adverse events (AE), measurement of vital signs, examination of the wound/site of wound, and notation of concomitant medication and procedures will also take place during each visit. All measures will be completed if an individual agrees to a final visit after withdrawal from the study.

Masking

This study will be an open-label study.

Schedule of Events

Baseline Testing (All subjects)

- Photographs (prior to start of treatment)
- Vital signs (e.g., blood pressure, heart rate, temperature, height, weight)
- Examination of wound, including wound measurement
- Concomitant medications
- VAS pain score before and after dressing application

Discharge

- Adverse events

- Vital signs
- Examination of wound, including wound measurement and percent reepithelialization
- Photography of treatment site
- Concomitant medications and procedures
- Dressing change
- VAS pain score before and after dressing change

Day 7, 21 (± 3 , Remote visit)

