Subjects will receive the study dressings (i.e., KeraStat Gel and KeraStat Gel-related secondary dressings) at no cost during the study. Based on initial performance testing in animals, burn wounds randomized to receive KeraStat Gel treatment may benefit from improved cosmesis, improved healing rates, reduced fibrosis and contraction, and no increase in infection rates compared to Mepilex Ag. Subjects will also be seen in the clinic regularly for visits and may gain more information about management of their condition. We hope the information learned from this study will benefit burn patients and clinicians in the future.

Subject Benefit to Participation in the Study

There are no identifiable direct benefits to participating in this study. However, there are some *potential* benefits to participation. Given that the burns will be examined more often than what is many times the typical approach, there is a potentially reduced risk of infection. Additionally, there is the potential for more rapid healing of the study burns treated with KeraStat.

Reporting of Unanticipated Problems, Adverse Events or Deviations

Any unanticipated problems, serious and unexpected AEs, deviations, or protocol changes will be promptly reported by the Principal Investigator or designated member of the research team to the Institutional Review Board (IRB) and Sponsor or appropriate government agency if appropriate.

An AE is defined as any unfavorable or unintended change in body structure, body function, laboratory result (e.g., chemistry, ECG), or worsening of a pre-existing condition associated temporally with the use of the test product, whether or not considered related to the test product. All AE will be recorded in the Case Report Form (CRF), and a cumulative total will be evaluated for each subject and across all subjects treated. AE and concomitant medications will be reported based on the MedDRA dictionary and evaluated for relationship to KeraStat Gel or dressing-related procedures. Any AE not requiring intervention will be reported at the discretion of the Investigator. AE, concomitant medications, and vital signs will be monitored and recorded at each study visit. Concomitant procedures will be assessed.

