AEs that are anticipated for this subject population include: neurological/psychological, cardiovascular, pulmonary, gastrointestinal, genitourinary, renal, musculoskeletal, blood, endocrine, skin/wound, infectious, eye/ear/nose/throat, chemical, and hematological complications.

While these events may be temporally associated with study participation, they are consistent with severe burns and may not be considered related to the study under most circumstances. An Investigator (to include other qualified study staff) will be responsible for evaluating individual

subjects and determining whether a specific event is potentially study-related or whether the event could be reasonably anticipated as normal sequelae of the subject's clinical status, injury, and hospital course.

In the event of an AE, the Investigator will use accepted institutional SOC guidelines (medical or surgical), as needed. Expected or unexpected AE will be managed according to institutional SOC guidelines.

All subjects will be treated to alleviate signs and symptoms as appropriate medical intervention dictates. All procedures or medical therapies related to treatment of the complication will be recorded. Investigator assessment of reasons for failure and medical/surgical management will be recorded in the CRF. Subjects who are discontinued from study treatment will remain in the study for safety assessments and efficacy analysis.

All AE will be recorded on the CRF. The time of the onset, location, duration, intensity, relationship to the test product, treatment, and follow-up will also be captured on the CRF. The relationship between the application of KeraStat Gel and the AE will be determined by the Investigator as 'not related' or 'related'. Events other than 'not related' will be considered related in the clinical study report.

Not related: The event is most likely produced by other factors such as the subject's clinical condition, intercurrent illness, or concomitant medications or procedures and does not follow a known response pattern to the study device, or the temporal relationship of the event to study device administration makes a causal relationship unlikely.

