Related: This relationship suggests that a reasonable temporal sequence of the event with device administration exists and, based upon known or previously reported adverse reactions to the device or class of devices or judgment based on the Investigator's clinical experience, the association of the event with the study device seems likely.

The severity (intensity) of AE will be graded according to the following definitions:

Mild: The subject experiences awareness of symptoms but these are easily tolerated or managed without specific treatment.

Moderate: The subject experiences enough discomfort to cause interference with usual activity, and/or the condition requires specific treatment.

Severe: The subject is incapacitated with inability to work or do usual activity and/or the event requires significant treatment measures.

An unexpected AE is one that is not consistent with the subject's past medical or acute burn history and is not evident from previous clinical experience with the test product or reasonably anticipated from pre-clinical information. An AE will be classified as 'serious' when it refers to any event during the 12-month study period that results in any of the following:

- Death
- Life-threatening adverse experience (i.e., the subject was at immediate risk of death from the reaction as it occurred)

- Inpatient hospitalization or prolongation of existing hospitalization
- Persistent or significant disability or incapacity
- A medically significant event or one requiring intervention to prevent one of the outcomes listed above and suspected to be due to the test product

All SAE will be followed until stabilization or improvement.

Clinical site personnel will be trained to follow study processes for reporting SAE. SAE reports will be managed by the clinical research team. The Principal Investigator will manage the process of ensuring that reports are completed appropriately and forwarded in a timely manner to all required recipients. The Principal Investigator will also assess individual and accumulating SAEs, AEs, and other safety data on a regular basis to identify any safety signals that should be brought to the attention of the Sponsor, , IRB offices, and/or the FDA.

Reporting for SAE which **are expected and not related** to KeraStat Gel will be as follows:

- The Principal Investigator (PI) will be notified within 24 hours of the Investigator becoming aware of any SAE that is expected or not related to the test product.

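### The protocol leaves AEs that need no intervention to the investigator's discretion without saying whether that covers CRF entry, the AE summaries or only onward notification, so mild events may be lost, possibly unevenly by dressing

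*Combined protocol and SAP*

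**What the plan says.** All of the AE rules below stand in the protocol section on Reporting of Unanticipated Problems, Adverse Events or Deviations.

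- **Recording, first statement:** "All AE will be recorded in the Case Report Form (CRF), and a cumulative total will be evaluated for each subject and across all subjects".
- **Coding:** "AE and concomitant medications will be reported based on the MedDRA dictionary".
- **Discretion, directly after the coding sentence:** "Any AE not requiring intervention will be reported at the discretion of the Investigator".
- **Visits, directly after the discretion sentence:** "AE, concomitant medications, and vital signs will be monitored and recorded at each study visit".
- **Recording, second statement, later in the section:** "All AE will be recorded on the CRF". Onset, location, duration, intensity and relationship to the product are captured with each event.
- **Lowest severity grade:** "Mild: The subject experiences awareness of symptoms but these are easily tolerated or managed without specific treatment".

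The Masking paragraph says: "This study will be an open-label study". The Analytical Plan summarises AE incidence by treatment group.

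**The concern.** One sentence makes a class of AEs discretionary in a section that otherwise requires every AE to be recorded. No criterion guides the discretion, and no rule says which statement governs an event that needs no intervention.

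The events affected are the ones most likely to show a local reaction to a dressing. The protocol's ISO 10993 table lists a mild to moderate irritant result in rabbits. Its Risks and Benefits section says some subjects may experience irritation, although it also cites a human repeat patch test pointing to a non-irritant product. Complete capture of mild local events is how this trial could help to settle that question.

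The investigator knows which burn carries which dressing, and no masked review of AEs is described. If the discretion reaches the CRF or the AE tables, two things are at stake: the absolute incidence of mild events and, for events that belong to one burn, the comparison of dressings.

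**Working it through.** This is mainly a check of the text. The arithmetic only illustrates possible size.

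**Step 1. What can *reported* mean?** The text supports three readings and states none of them.

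| Reading | Support | Difficulty |
|---|---|---|
| Entry on the CRF | The sentence sits between the coding sentence and the visit-recording sentence, in a paragraph about data capture | Contradicts both all-AE recording statements and the visit-recording sentence |
| Inclusion in AE summaries | The preceding sentence uses the same verb for MedDRA-based output, and the Analytical Plan uses it for incidence by treatment | Conflicts with the cumulative total of all AEs and with incidence tables that carry no such exclusion |
| Notification of the IRB or sponsor | The section heading and its opening paragraph concern notification, and capture is elsewhere described with *recorded* | Near its end the same section says AEs shall be promptly reported to the IRB under institutional policy, with no exemption for events needing no intervention |

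Each reading conflicts with some other sentence, so the wording needs reconciling whichever was meant.

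**Step 2. Which events are covered?** The mild grade is defined as "The subject experiences awareness of symptoms but these are easily tolerated or managed without specific treatment", so most mild events need no intervention. The moderate grade can be met by interference with usual activity alone, so some moderate events are covered too.

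**Step 3. Which of these can affect the comparison?** Each subject receives both dressings. Only an event located to Burn A or Burn B can be attributed to a dressing. A mild systemic event belongs to a subject exposed to both.

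**Step 4. Illustrative size.** The Sample Size paragraph gives 30 subjects × 2 wounds = 60 wounds, 30 per treatment, which reproduces. The documents give no AE rate, so everything else here is assumed. Let *p* be the same true rate of mild local AEs on both dressings, and let *r* be the fraction reported on each.

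Expected reported count = 30 × *p* × *r*. The apparent incidence ratio is *r*(gel) / *r*(Mepilex Ag), whatever the value of *p*.

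| True rate | Reported, Mepilex Ag / gel | Expected counts | Apparent ratio | Chance the gel count is lower |
|---|---|---|---|---|
| 20% | 100% / 100% | 6.0 / 6.0 | 1.00 | 0.44 |
| 20% | 100% / 75% | 6.0 / 4.5 | 0.75 | 0.63 |
| 20% | 100% / 50% | 6.0 / 3.0 | 0.50 | 0.82 |
| 20% | 75% / 75% | 4.5 / 4.5 | 1.00 | 0.43 |
| 40% | 100% / 100% | 12.0 / 12.0 | 1.00 | 0.45 |
| 40% | 100% / 75% | 12.0 / 9.0 | 0.75 | 0.75 |
| 40% | 100% / 50% | 12.0 / 6.0 | 0.50 | 0.94 |
| 40% | 75% / 75% | 9.0 / 9.0 | 1.00 | 0.44 |

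The last column treats all wounds as independent binomial observations, which ignores the pairing within subjects. The direction of the split is arbitrary, and reversing it would count against the gel.

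The rows with equal reporting below 100% show the other effect. The ratio stays at 1.00, but a true 20% appears as 4.5/30 = 15%, and a true 40% as 9.0/30 = 30%.

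**The case against.** The best counter-argument is that the protocol uses two verbs for two acts. Events are *recorded* on the CRF, without exception for mild ones, and *reported* to the IRB and sponsor. The heading and opening paragraph of the section fit this, and the sentence straight after the disputed one requires AEs to be recorded at each visit. On that reading capture is complete. This is plausible, but the text never says it, the adjacent coding sentence uses *reported* for study data, and the later IRB rule leaves no obvious room for discretion.

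Second, safeguards exist. The Analytical Plan promises listings of all CRF data. Pain, infection, reepithelialization and photographs are collected for each burn on days 14 and 28 whatever is done about AEs. These make it harder for a local effect to go unseen. But listings show only what was entered, and the wound assessments do not replace an AE record. A later SAP could define which recorded events enter the tables, but it could not recover events never entered.

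Third, staff in any open-label trial judge what counts as an AE, and AE incidence here is a descriptive summary rather than a stated primary or secondary objective. Both points are true and limit the weight of this one. Removing the sentence would not remove unmasked judgement, but it would remove an apparent licence to omit events already recognised as AEs.

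A reader might go further and infer that the protocol authorises investigators to keep mild AEs off the CRF, or that the comparison of dressings will be biased. The documents support neither. The first needs one ambiguous verb to override three recording statements. The second also needs the discretion to be used differently on the two burns, and nothing in the documents shows that it would be.

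**Conclusion.** The conflict in the wording is real and should be resolved. The documents do not establish a rule of selective capture. They leave one open under a reading that the text allows.

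If *reported* covers CRF entry or the summaries, the incidence of mild and some moderate AEs is understated by whatever fraction is left out. For events located to one burn, the apparent incidence ratio moves from 1.0 to the ratio of the two reporting fractions: 0.75 and 0.50 in the assumed cases. Those values follow entirely from the assumed fractions and are not estimates for this trial. Equal use of the discretion does not bias the ratio, and systemic events do not enter the comparison of dressings. If *reported* means onward notification only, there is no effect on the AE tables, and what remains is a conflict with the institutional-policy rule for IRB reporting.

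The point concerns the safety summary and leaves the primary objective untouched.

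**What to change.** Delete the discretion sentence, or replace it with wording to this effect: every AE, whether or not it requires intervention, is entered on the CRF, with the burn site (Burn A or Burn B) where applicable, and is included in the AE listings and incidence summaries; any discretion is limited to onward notification of non-serious AEs and is subject to institutional policy.

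Reconcile that last clause with the statement near the end of the same section that AEs are promptly reported to the IRB according to institutional policy. The SAP should repeat the rule on which events enter the tables, and should present AEs located to one burn by dressing and systemic AEs by subject.

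The cost is one sentence in the protocol, a line in the SAP and a few more mild AE entries. Design, sample size and clinical management do not change.

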Below is a schematic overview of the study.

Optional at-home questionnaire and photographs at virtual visits on weeks 1 and 3

Wound assessments, questionnaires, photographs, TEWL assessment at 3 months, 6 months, 1 year

Setting

This study will be conducted in the Wake Forest (WF) Burn Center and in the University Medical Center New Orleans (UMC). Subjects may continue treatment as inpatients or as outpatients.

Subjects Selection Criteria

- **Inclusion Criteria**

- Males and females, age 6 years and older
- Written informed consent and assent, if applicable (including parent if subject is a minor)
- Presenting with at least two comparable, discrete, and separate partial thickness thermal burns, as determined by the Investigator, measuring 50-1,000 cm² each
- Study wounds identified are partial thickness depth
- KeraStat Gel and Mepilex Ag can be applied to the randomized study burn wounds as definitive care treatment within 72 hours from time of injury
- Overall total body surface area (TBSA) burned < 20%

- **Exclusion Criteria**

- Pregnant or nursing
- Prisoner
- Presence of inhalation injury, as determined by the Investigator
- Injury requiring formal intravenous fluid resuscitation
- Concomitant non-thermal traumatic injuries
- Chronic medical conditions including, but not limited to, documented > renal impairment (Cr > 2.5 mg/dL), hepatic impairment (Total bilirubin > 2.5 mg/dL), thromboembolic disorders, active infection in study wound areas, uncontrolled diabetes (HbA1C > 7%), HIV infection, history of melanoma or systemic malignancy within the last 10 years
- Receiving corticosteroids, immunosuppressive agents, radiation or chemotherapy, topical growth factors, or any other medication the Investigator feels will affect wound healing
- Not expected to live at least 13 months post-burn
- Previously treated with a skin graft at either of the treatment sites

- Chemical or electrical burn
- Proposed study wounds are full thickness
- Any condition the Investigator determines will compromise subject safety or prevent the subject from completing the study

- **Sample Size**
The study size is 30 subjects, two wounds per subject, 30 wounds per treatment cohort resulting in 60 total wounds.

Because this trial is designed to examine long-term outcomes, no interim analyses or stopping rules are planned.

Interventions and Interactions

Intervention: KeraStat Gel

Agent description

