The Research Monitor, [name], III, MD FACS is responsible to oversee the safety of the research and report observations/findings to the IRB or a designated institutional official. The Research Monitor will review all unanticipated problems involving risks to subjects or others associated with the protocol and provide an independent report of the event to the IRB. The Research Monitor may discuss the research protocol with the investigators; shall have authority to stop a research protocol in progress, remove individual human subjects from a research protocol, and take whatever steps are necessary to protect the safety and well-being of human subjects until the IRB can assess the monitor’s report; and shall have the responsibility to promptly report their observations and findings to the IRB or other designated official.

Risks and Benefits

There are no known risks associated with using KeraStat Gel. ISO 10993 testing supports the safety of the product. ISO 10993-10 testing suggested that some subjects may experience irritation; however, a GLP preclinical study and a human repeat patch test indicate the product is a non-irritant. A human skin prick test found that the product does not elicit an allergic response. The currently known risks associated with participation in this study include: discomfort at the wound site, infection at the wound site, lack of wound closure, and an allergic reaction to the dressings, sedatives, narcotics, or any other drugs which might be administered concomitantly with the procedure. All subjects will be given information on potential side effects and will be offered the option of alternative treatments by the Investigator prior to enrolling in the study. There may also be other side effects that we cannot predict or are not known. Taking part in this research study may involve providing information that subjects consider confidential or private. Efforts, such as coding research records, keeping research records secure, and allowing only

authorized people to have access to research records, will be made to keep subject information safe.

Alternative treatments include but are not limited to other topical (applied to the skin) dressings, such as silver sulfadiazine or triple antibiotic ointment or saline-soaked gauze.

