- The PI will promptly notify the Sponsor, the local IRB office and the central IRB office of all SAE.
- The Investigator will complete an SAE form and send it to all IRB offices and Sponsor within ten days of the SAE.

Reporting for an SAE that is determined to be **both unexpected and deemed related** to KeraStat Gel treatment will be as follows:

- SAE that are both unexpected and possibly or probably related to the test product will be reported within 24 hours of the Investigator becoming aware of the event via telephone, facsimile, or e-mail to the PI.
- The PI will notify the Sponsor, the local IRB office, and the central IRB office of all SAE within 72 hours of learning of the SAE.
- The Investigator will send the SAE report to all IRB offices and Sponsor within ten days of the SAE.
- The Sponsor will submit the SAE report to all Investigators and will submit the FDA MedWatch report to the FDA.
 - Within 7 calendar days for fatal or life-threatening SAE
 - Within 15 calendar days for all other unexpected and related SAE

Any unanticipated problems involving risks to subjects or others and AEs shall be promptly reported to the IRB, according to institutional policy. Reporting to the IRB is required regardless of the funding source, study Sponsor, or whether the event involves an investigational or marketed drug, biologic or device. Reportable events are not limited to physical injury, but include psychological, economic and social harm. Reportable events may arise as a result of drugs, biological agents, devices, procedures or other interventions, or as a result of questionnaires, surveys, observations or other interactions with research subjects.

All members of the research team are responsible for the appropriate reporting to the IRB and other applicable parties of unanticipated problems involving risk to subjects or others. The PI, however, is ultimately responsible for ensuring the prompt reporting of unanticipated problems involving risk to subjects or others to the IRB. The PI is also responsible for ensuring that all reported unanticipated risks to subjects and others that they receive are reviewed to determine whether the report represents a change in the risks and/or benefits to study subjects, and whether any changes in the informed consent, protocol or other study-related documents are required.

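### The adverse-event section presumes broad classes of event, study-wound events included, to be mostly unrelated because of severe burns; this fits neither the eligibility criteria nor the protocol's own list of participation risks

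*Combined protocol and SAP*

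**What the plan says.** Under Reporting of Unanticipated Problems, Adverse Events or Deviations, the protocol gives a list that begins "AEs that are anticipated for this subject population include: neurological/psychological, cardiovascular, pulmonary, gastrointestinal, genitourinary, renal, musculoskeletal" and continues through blood, endocrine, skin/wound, infectious, eye/ear/nose/throat, chemical and hematological complications. The next sentence allows that such events may coincide in time with participation, but says that "they are consistent with severe burns and may not be considered related to the study under most circumstances". The Investigator is then asked to judge, subject by subject, whether an event may be study-related or is a normal consequence of that subject's status, injury and hospital course.

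Two other sections bear on this:

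- **Subjects Selection Criteria** caps burn extent ("Overall total body surface area (TBSA) burned < 20"%), requires that "Study wounds identified are partial thickness depth", and excludes inhalation injury, full-thickness study wounds and "Injury requiring formal intravenous fluid resuscitation".
- **Risks and Benefits** states: "The currently known risks associated with participation in this study include: discomfort at the wound site, infection at the wound site, lack of wound closure". It also lists allergic reaction.

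**The concern.** A statement that whole classes of event are usually unrelated needs a reason that fits the people enrolled. The reason given is the severity of the burns, and the entry criteria describe a more limited injury. The presumption also covers skin/wound and infectious events. For a topical dressing these are the events most informative about safety, and another section of the same protocol treats two of them as risks of taking part.

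At stake are the Investigator's causality judgements and what follows from them: the count of related AEs in the study report, and the reporting steps reserved for SAEs that are both unexpected and related. Attribution carries extra weight in this design. The trial is open-label and every subject receives both dressings, so a systemic event cannot be compared between arms and its link to the gel rests largely on the Investigator's opinion.

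**Working it through.** No arithmetic applies beyond a count; the check sets the sections side by side.

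**1. Breadth of the list.** The categories are neurological/psychological, cardiovascular, pulmonary, gastrointestinal, genitourinary, renal, musculoskeletal, blood, endocrine, skin/wound, infectious, eye/ear/nose/throat, chemical and hematological: 14, with some overlap (blood and hematological). None comes with event terms, severity or rates.

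**2. Rationale against eligibility.** The rationale rests on severe burns, a term the protocol never defines. The criteria admit a burned area under 20% without inhalation injury or formal fluid resuscitation, and study wounds of partial thickness. The Design section does not require an overnight stay and expects closure within 21 days where grafting is not needed. The rationale does not describe this population well. Two limits apply: the depth restriction covers only the study wounds, so other burns may be deeper, and no criterion uses the word severe.

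**3. Presumption against known risks.** Risks and Benefits lists wound-site infection and lack of closure as risks of participation. The AE section puts skin/wound and infectious events among those presumed mostly unrelated to the study. This conflict does not depend on what severe means.

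**4. How the label is decided.** Relatedness is binary, under written definitions of related and not related; anything other than not related counts as related in the study report. An event is unexpected if it is inconsistent with the subject's own medical or acute burn history and is not foreseen from clinical or pre-clinical experience with the product. None of these definitions cites the list. The presumption therefore acts by influencing judgement, not by rule.

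**5. What the label changes for an SAE.**

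| Step | Expected or not related | Both unexpected and related |
|---|---|---|
| Investigator to PI | 24 hours | 24 hours |
| PI to Sponsor and IRBs | promptly | 72 hours |
| SAE form or report to IRBs and Sponsor | ten days | ten days |
| Circulation to all Investigators | not stated | yes, by the Sponsor |
| MedWatch report to the FDA | not stated | 7 days if fatal or life-threatening, otherwise 15 |

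The right-hand column opens with "SAE that are both unexpected and possibly or probably related to the test product will be reported within 24 hours". The left-hand column follows the bullet that says expected *or* not related; the lead-in above that bullet says expected *and* not related. What depends on the label is the fixed 72-hour limit, circulation to Investigators and the FDA report.

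**6. Which events are exposed.** For a systemic SAE that is unexpected, a not-related label removes those three steps. A study-wound infection may be judged expected in any case, since it is a known risk; there the main effect is on the related-AE count.

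**The case against.** The case against is substantial. The wording is hedged, and an instruction to assess each subject individually follows at once. Relatedness and expectedness have their own definitions. All SAEs reach the PI, Sponsor and IRBs whatever the label. AE incidence is to be summarised by treatment group regardless of causality, and infection is recorded for each burn at days 14 and 28, so local events can be compared within subject without attribution. The PI reviews accumulating safety data for signals, and a Research Monitor reviews unanticipated problems.

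Most of this stands, and it rules out several stronger readings that a reader might infer:

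- *That the criteria exclude severe burns.* The term is undefined and non-study burns are not restricted by depth. The rationale does not match the population; more than that cannot be shown.
- *That any listed SAE can be classed as expected.* The definition of unexpected turns on the subject's history and product experience, not on the list.
- *That these events escape expedited reporting altogether.* Only the three steps identified above depend on the label.
- *That the number of listed categories can be set against the number of known risks.* Organ-system classes and specific risks are different kinds of item.

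The objection does not remove the presumption itself. The individual assessment asks what could reasonably be anticipated directly after a sentence that calls nearly every body system anticipated. The definition of not related appeals to the subject's clinical condition, and the definition of related requires that an association seem likely. With two categories and a stated lean, borderline events could fall to not related. Nor do the safeguards resolve the conflict with Risks and Benefits.

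**Conclusion.** The concern holds in a limited form. The stated reason for presuming non-relatedness does not match the enrolled population, and the presumption conflicts with the protocol's own list of participation risks for wound infection and non-closure. It could tilt causality towards not related, most of all for study-wound events. That would lower the related-AE count and, for an SAE that would otherwise be unexpected and related, remove the 72-hour limit, circulation to Investigators and the FDA report.

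The size cannot be given: the documents contain no event rates, and a downward bias is a risk, not an established fact. The conclusion assumes that Investigators give the sentence some weight, and that the bullet covering expected or not-related SAEs governs mixed cases. The change is worth making because it is cheap and because systemic events have no between-arm comparison to fall back on.

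**What to change.** 1. Delete the statement that "they are consistent with severe burns and may not be considered related to the study under most circumstances", together with the clause that introduces it, which would otherwise be left hanging.
2. State that being on the anticipated list does not decide relatedness, and that each event, study-wound events in particular, is judged under the protocol's existing definitions of related, not related and unexpected.
3. Reconcile the list with Subjects Selection Criteria and with Risks and Benefits, so that the three sections describe the same population and the same risks.

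No new rule that unexplained systemic events are unexpected is needed; the existing definition already covers them. The cost is protocol wording and possibly a few more expedited reports among 30 subjects.
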